1.8 Dose Rationale

The selection of the dose proposed for the Phase 3 trial is based on the converging evidence provided by the following:

- Phase 2 Dose Finding trial (GLY-311-2017)
- Phase 2 Proof of Mechanism trial (GLY-321-2017)
- Pharmacology results from Healthy Volunteer trials (GYM-P3-698 and TA799-002)
- Safety margins (from GLP toxicology studies)
- Population pharmacokinetic model

In the Phase 2 trial GLY-311-2017, 5 mg and 10 mg weekly doses of apraglutide were tested against placebo in SBS-IF patients. The key efficacy outcome was the ambulatory urinary output measured during a 48-hour fluid balance period. Under these conditions, urinary output is used as a surrogate marker of intestinal absorption. The average change in urinary output from baseline at 5 mg and 10 mg doses against the placebo period was an increase of 48.5% for the lower dose and 32.6% for the higher dose. In conclusion, the urinary output increased at both doses against placebo although it did not increase from 5 to 10 mg, whereas generally apraglutide was safe and well tolerated at both dose levels.

The second Phase 2 trial GLY-321-2017 showed increases in urinary output (surrogate marker of intestinal fluid absorption), wet weight intestinal absorption, and intestinal energy absorption at a dose of 5 mg once weekly. Therefore, the GLY-321-2017 trial further supports the adequacy of the proposed dose of weekly 5 mg subcutaneous injection.

Moreover, in the Phase 1 trial (GYM-P3-698), apraglutide was shown to be safe and well tolerated up to 56.9 mg after single SC doses and up to 56.9 mg when dosed weekly after three doses. Pharmacokinetics were proportional to dose at the tested dose range. The PD marker citrulline was induced after three weekly doses of apraglutide with similar response from 11.4 to 56.9 mg, suggesting that at 11.4 mg weekly an effect on citrulline also becomes saturated.

Results from TA799-002 showed that 5 mg weekly dosing of apraglutide induced significant increases in citrulline levels; steady state levels were reached at Week 2 and remained elevated with 5 mg weekly dosing, supporting that at a dose regimen of 5 mg once weekly apraglutide will sustain biological effects for at least 1 week. No statistically significant difference in plasma citrulline levels was observed between 5 mg and 10 mg doses.

The exposure margins at the no-observed-adverse-effects level (NOAEL) in the repeat-dose toxicity studies are well in excess of 200-fold in both rats and minipigs, and >40-fold at the NOAEL of 1 mg/kg/day in the 13-week mouse toxicity study relative to the exposure at the proposed clinical dose of 5 mg once a week subcutaneous injection of apraglutide. The exposure margins for apraglutide at the

NOAEL in the embryofetal development studies in rat and rabbit are 140- and 17-fold, respectively, thereby advocating for the use of highly effective methods of contraception in this trial.

A PopPK model was developed which included data from all four clinical trials. Of all the tested covariates only body weight at baseline was statistically significant, with body weight inversely correlating with area under the curve (AUC) and maximum observed plasma concentration (C_{max}). Due to the higher, non-linear increase of exposures (AUC and C_{max}) as body weight decreases, subjects with body weight below 50 kg will be dosed with 2.5 mg to prevent high exposures and mitigate safety risks. Alternatively, subjects of 50 kg or higher body weight will receive 5 mg.

Although some heavy subjects may get lower exposures, it is estimated that the number of patients with SBS and heavy body weight is minimal (see for example body weight distribution in [STEPS trial](#); [Jeppesen, 2012](#); [Jeppesen, 2018](#)).

In conclusion, taking together all data available (nonclinical data, clinical PK, PD, safety, and clinical efficacy data from adult SBS-IF subjects) and the higher exposure in low body weight subjects, 5 mg once a week subcutaneous injection of apraglutide is proposed as the clinical dose for subjects weighing 50 kg or more and 2.5 mg for subjects with body weight lower than 50 kg.

2. TRIAL DESIGN

2.1 Rationale for the Trial Design

Completed trials investigating the effects of apraglutide enrolled subjects with stoma, whilst the ongoing blinded Phase 3 trial, TA799-007, is enrolling subjects with both stoma and CIC. The current trial will examine the safety profile of apraglutide in CIC subjects, over 1 year in an open label trial. Data from the current trial will be important for ongoing clinical trials to determine if there are differences in the safety profile of apraglutide between CIC and stoma subjects.

Balance studies quantify weight, volume, as well as the content of energy, macronutrients and electrolytes of oral intake (i.e., food and fluid intake, as well as PS) and of the output (i.e., feces and urine production). Balance studies are acknowledged as the “gold standard” to measure intestinal function and the methods used have been published [\[Jeppesen, 2013\]](#)

Wet weight excretion is an important secondary endpoint of this trial. Fecal output is important to assess since it is closely linked to the intestinal function and degree of malabsorption. Urinary output is another important secondary endpoint of this trial. Patients with SBS are at high risk of sodium depletion and dehydration and maintaining a proper hydration state is essential.

Sodium, and hence water, are avidly conserved by the kidney, so the hydration state of the patient can be monitored by measuring the urinary output and the urinary sodium concentration. In SBS patients, increases in urinary output and urinary sodium concentration are markers of functional intestinal rehabilitation [\[Jeppesen 2014\]](#).

A previous balance study has been performed using apraglutide ([GLY-321-2017](#)); however, all enrolled patients had either ileostomy or end-jejunostomy. The current study will enroll exclusively CIC patients, which may have different outcomes in the proposed endpoints. The previous study demonstrated a change in fecal excretion over the 4-week treatment period including a decreased sodium ostomy output and increased absorption of energy, fat, carbohydrate, etc. However, this previous study did not look at effects beyond the 4-week treatment period.

Studies examining the use of another GLP-2 analog, teduglutide, have demonstrated that CIC patients may have a different response to treatment. It was found that CIC may be weaned off PS support but had less of a volume of PS reduction versus patients with a stoma, reflecting the lower baseline PS volume [\[Joly, 2020\]](#).

Thus, the current clinical trial will examine the effect of apraglutide on metabolic parameters in CIC patients over a longer period time than previous studies. As CIC patients make up a large proportion of the SBS population it is important to investigate the effects of apraglutide in this population.

2.1.1 Rationale for the PS Volume Reduction Algorithm

In a previous 24-week treatment Phase 3 trial with the GLP-2 analog teduglutide, PS volume could be reduced by 10% at clinical visits, if urinary output increased by at least 10% [\[Jeppesen, 2011\]](#). Many subjects in this trial suffered from fluid overload and stopped drinking. In a follow-up Phase 3 trial (STEPS trial) PS volume reductions of at least 10%, but not more than 30% were allowed, if urinary output increased by

at least 10% [Jeppesen, 2012].

[REDACTED] These fluid overloads were the results of strong drug effects on intestinal absorption that cannot be followed by adequate reductions in PS.

In the TA799-013 trial, PS volume adjustments will be performed after an increase of at least 10% of urinary output against baseline value by calculating a new PS volume (Section 4.5). This approach enables adjustment of PS volume with a lower likelihood of fluid overload.

The urinary output driven algorithm will be further expanded to include a clinical assessment of subjects which includes body weight, stools (consistency, frequency, etc.), a physician narrative of the overall well-being, oral food intake including appetite, fluid intake (oral drinking volume and PS) and daily urinary volume from 48-hour balance period which may lead to further reduction in PS.

2.2 Overall Design

This is an international, multicenter, open-label metabolic balance study to evaluate the efficacy and safety of apraglutide and effects on intestinal absorption in adult subjects with SBS-IF and CIC.

After provision of informed consent and initial confirmation of eligibility, subjects will be screened (Table 1). If they meet the eligibility criteria, they will return to site for the Baseline metabolic balance period as per Table 1. They will remain at site to complete the metabolic balance study. Dosing eligibility criteria will be confirmed after completion of the baseline metabolic balance study and before the first dose of investigational medicinal product (IMP). Subjects will return to the site on Day 0 for the first dose of IMP.

Subjects will receive a SC dose of 2.5 mg or 5 mg apraglutide once weekly for 52 weeks. Safety follow-up assessments will be performed 4 weeks (± 1 week) after the last dose.

Between visits, IMP can be either self-administered at home or by a family member/caregiver, or administered at the clinic. The capabilities of the subject to self-administer the IMP will be assessed by the site after training the subject or family member/caregiver in SC administration of IMP using a training kit. The decision to select IMP administration at site or at home will be determined based on subject capability for self-administration at home, subject preference and clinical considerations (Section 4.2.1). The subject will record IMP self-administration information in their e-diary (Section 5.1.7).

If the daily urine volume of the balance period prior to the current visit is at least 10% higher than the baseline urine volume, then the weekly PS volume will be reduced as detailed in Section 2.1.1.

If the daily urine volume of the balance period prior to the current visit is less than 10% greater than baseline values, the subject's clinical status will be reviewed by all three Investigators. If in the treating Investigator's opinion an adjustment is warranted, the proposed adjustment will be sent to the other Investigators for review. Within 7 days the other Investigators will review and send their recommendation. Recommendations will be made for the safety of subjects and with the objective to standardize and harmonize decisions on PS volume reduction and weaning across the three sites.

If there is a discrepancy between the proposed adjustment by the treating Investigator and the other Investigators a telephone/video conference will be held within 7 days to resolve the differences. If no unanimous decision can be reached the treating Investigator's recommendation will be used. Final decision and summary of conferences will be filed in the subject's medical record. The treating Investigator will provide a rationale within the electronic case report form (eCRF) indicating why and which course of action was followed.

In this trial the following applies:

- 1) Parenteral support is defined as any intravenous infusion that contains fluids and electrolytes and may or may not include parenteral nutrition (PN).
Parenteral nutrition is defined as PS that includes protein, carbohydrate, fat, vitamins, and/or trace elements
- 2) Fluids consumed during the balance period may be taken either by mouth or via GI tube, naso-jejunal tube, gastrostomy tube, or other type of permanent or temporary tube
- 3) Fluid is defined as any liquid which does not contain solids (e.g., water, soda, juice, and clear broth). If the fluid contains solids it should not be considered a liquid (e.g., soup with vegetables, noodles, and rice). Smoothies, blitzed meals, yoghurt, puddings, etc. are also considered food not fluids
- 4) Subjects must receive PS at least 2 times a week to be eligible for the trial.
There is no minimum volume required per day but PS must be necessary for the medical treatment of the subject. An infusion of a small amount of fluid to maintain catheter patency is not considered PS
- 5) The volume of each urine void needs to be measured and recorded in the diary on an ongoing basis over the 48-hour balance period and will not be collected into a single container over the balance period. Further details are included in the Laboratory manual
- 6) During the trial, if the days of PS are reduced, then the 48-hour balance period should contain 1 day of PS support and one day without, if possible. If a subject has been weaned completely from PS, the balance period will not contain any days of PS

2.2.1 Screening Period

Initial Screening Visit

Potential subjects will be approached by the Investigator and the trial will be explained to them. It is recommended that the Investigator verifies if the subject has a history of vomiting on a frequent basis or a history of obstruction.

After obtaining informed consent, subject initial eligibility will be evaluated (Section 3.2).

All initial eligibility criteria must be met for the subject to be allowed to enter the baseline period.

If the remaining small bowel length is not specifically and clearly documented within the site's medical/surgical records to conclusively demonstrate that the small intestine is <200 cm, the Investigator will use their clinical judgement along with available surgical/medical records, to determine if the subject meets this criterion. The Investigator may also conduct additional investigations (e.g., imagistic or

endoscopic evaluations), if needed in their clinical opinion. This will be documented in the subject's site file and in the eligibility package sent to the medical monitor.

In collaboration with the Investigator, the subject will select an individual drinking menu which will have to be adhered to for all further fluid balance assessments during the course of the trial. The drinking volume must be ≥ 1.0 L and ≤ 3.5 L/day. A deviation during the 48-hour balance periods of $\pm 10\%$ to the defined menu is acceptable.

Subjects will receive the e-diary and the baseline metabolic balance evaluation visit will be scheduled.

After Screening, eligible subjects will be given a patient card supplied by the Sponsor that will provide information required in an emergency situation; for example, the protocol number, trial title, product name, Sponsor name and address, Investigator site's 24 hour telephone number, and the emergency contact details for the subject.

Baseline Period

Prior to subjects receiving their first dose of trial medication, they will be admitted and confined to the site for 5 days to perform the baseline metabolic evaluation. During this time the individual drinking menu and dosing eligibility criteria (average fecal wet weight excretion of ≥ 500 g/day and average urine volume of ≥ 0.8 L and ≤ 2.5 L per day) will be confirmed.

2.2.2 Treatment Period

All eligible subjects will begin treatment after screening and baseline period assessments have been performed. The IMP (apraglutide) should be administered on the same day of the week based on the first administration at Week 0 (Visit 3), with a window of ± 24 hours, i.e., the administration could be performed up to 24 hours earlier or later than the scheduled day. For example, if the first dosing is done on a Tuesday, the following IMP administrations can be performed on Mondays, Tuesdays or Wednesdays. When the subject is admitted for the metabolic balance periods (Weeks 4 and 48), IMP will be administered as per [Table 1](#) and [Table 2](#).

Detailed instructions will be provided in the Trial Medication Manual for Subjects, and a Subject Visit Plan will be provided.

The IMP can be self-administered by the subject at home, as detailed in [Section 4.2.1](#). When a subject attends site for a scheduled visit, the IMP administration must be done in the clinic to allow for appropriate scheduling of administration-related assessments ([Table 1](#) and [Table 2](#)).

During the treatment period, visits take place 2 and 4 weeks after the first dose and then every 4 weeks ± 1 week, with the final visit of the treatment period (Visit 17) taking place at Week 52 ± 2 days. On Weeks 4 and 48 (Visits 5 and 16), subjects will be admitted and confined to the trial site for 5 days to complete the metabolic study. During the first week, after first dose of IMP, telephone contact must be made with the subject, to detect any signs of fluid overload.

Prior to each visit (except for Weeks -1, 4, and 48 [Visits 2, 5, 16]) and End of Trial (EOT), the subject will collect data in an e-diary during 48-hour balance periods and adhere to the drinking menu as described above. In addition, the subject will record the PS details for the week prior to every visit. Except for the period up to the second

metabolic balance study at Week 4 (Visit 5), the PS volume can be adjusted, if the criteria for adjustment are met.

Subjects who meet individual stopping rules following IMP administration will be discontinued from the trial (Section 6.6.2).

The drinking menu must be adhered to during the 48-hour balance period and metabolic periods, but a deviation of $\pm 10\%$ to the defined volume is acceptable.

During the treatment period, Investigators are encouraged to increase the subject's enteral nutrition as appropriate. These changes can be entered into the Investigator Narrative.

2.2.3

Phase II Study of Apraglutide in SBS

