3.5 Withdrawal/Discontinuation of Subjects

Every effort should be made to keep all subjects in the trial.

In case a subject discontinues or withdraws prematurely from the trial treatment for any reason after receiving at least one dose of IMP, the subject should be asked to perform the early termination visit and continue participation in the trial as per the Schedule of Assessments (SoA), i.e., participating in all trial assessments according to the protocol (with the exception of IMP administration) until the planned Week 52 visit.

In cases where this is not possible, the subject should be asked if they would allow the Investigator to continue collecting their weekly PS prescription and/or actual PS administration data once a month (through a phone call to the subject) until what would have been the subject's planned Week 52 visit and to continue to collect the subject's safety data (AEs).

Investigators should observe subjects who discontinue IMP treatment for potential dehydration or fluid overload, and in such case, PS should be managed according to local clinical practice.

If a subject withdraws prior to receiving IMP, the early termination visit is not required.

² Subjects recovered from hepatitis B or C can be enrolled, i.e., they have markers of the infection, but the viral load is undetectable. Subjects with evidence of an acute or chronically active hepatitis B or C infection should be excluded. If a subject is positive for hepatitis A virus immunoglobulin M antibodies, this would indicate an acute infection and the subject is ineligible, but he/she may be eligible for re-screening after recovery. Patients with isolated hepatitis A virus IgG antibodies can be enrolled. A subject positive for hepatitis B antigens, along with an undetectable viral load and a history of vaccination against hepatitis B would be eligible for enrollment.

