4.9.2 Intent to Treat Follow-Up

All subjects will be asked to consent to be followed up even if they stop taking treatment early (Section 3.5).

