6.6.2 Individual Subject Stopping Rules

During the trial, liver toxicity will be monitored according to guidelines from the US Food and Drug Administration (FDA) (FDA Guidance for Industry: Drug-Induced Liver

Injury: Premarketing Clinical Evaluation, 2009) and treatment will be discontinued if any of the following stopping criteria are met for subjects with ALT and AST <1.5 ULN at baseline:

- Alanine aminotransferase or AST >8 × ULN once
- Alanine aminotransferase or AST >5 × ULN for more than 2 weeks
- Alanine aminotransferase or AST >3 × ULN and total bilirubin >2 × ULN or INR >1.5 for a person not using anticoagulant drug and INR >3 for a person on anticoagulant therapy such as warfarin.
- Alanine aminotransferase or AST >3 × ULN and clinical signs of fatigue, nausea, vomiting, right upper quadrant pain or tenderness, fever, rash, and/or eosinophilia

Patients with SBS-IF, who are dependent on PN, commonly develop abnormal liver function tests. This condition is known as intestinal failure-associated liver disease or PN-associated liver disease [Abu-Wasel, 2014]. In this case, ALT and or AST levels may be elevated at baseline; therefore, the stopping rules for these subjects have been adapted based on published guidelines [Treem, 2021]. For subjects with baseline AST and/or ALT values \geq 1.5 ULN, treatment will be discontinued if any of the following stopping criteria are met:

- Alanine aminotransferase or AST \geq 2 x baseline or 5 x ULN (whichever comes first) **AND** total bilirubin (TBL) \geq ULN (if normal at baseline) or TBL \geq 1.5 x baseline (if elevated at baseline)
- Alanine aminotransferase or AST \geq 2 x baseline or 5 x ULN (whichever comes first) **AND** INR \geq 1.5
- Alanine aminotransferase or AST \geq 3 x baseline or 8 x ULN (whichever comes first)
- Alkaline phosphatase \geq 2 x baseline and direct bilirubin 1 mg/dL (17.1 mol/L) over baseline

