The IMP should not be restarted until a diagnostic evaluation is completed. A re-challenge may be considered in case of IMP discontinuation due to meeting one of the above stopping criteria after a consultation and approval by the Medical Monitor. Additional visits to the site for un-scheduled laboratory samplings should be arranged in such a case, or the subject should see their local doctor for laboratory assessments as agreed with the Investigator. In case of abnormal laboratory results of CTCAE Grade 3 or higher as assessed by the subject's local doctor, a re-assessment should be scheduled at the site. All results will be filed in the medical chart, assessed by the Investigator, and entered in the eCRF accordingly.

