9.4 Early Termination of the Trial

The Sponsor may terminate the trial prematurely according to certain circumstances, for example:

- Ethical concerns
- Insufficient subject recruitment
- When the safety of the subjects is doubtful or at risk, respectively
- Alterations in accepted clinical practice that make the continuation of a clinical trial unwise
- Early evidence of benefit or harm of the experimental intervention

Individual subject stopping rules and trial stopping criteria are described in Section 6.6.2 and Section 6.6.3, respectively.

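### Protocol 2.2.2 takes a subject who meets a stopping rule out of the trial, but Section 6.6.2, which it cites, stops only the drug

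*Protocol*

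**What the plan says.** Section 2.2.2 of the protocol, on the treatment period, gives this instruction: "Subjects who meet individual stopping rules following IMP administration will be discontinued from the trial (Section 6.6.2".

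Section 6.6.2 holds the rules themselves, which are liver-function criteria in two sets according to baseline ALT and AST. Section 9.4 confirms the location: "Individual subject stopping rules and trial stopping criteria are described in Section 6.6.2 and Section 6.6.3, respectively". In 6.6.2 the consequence, given for both sets, is that "treatment will be discontinued if any of the following stopping criteria are met". The section then looks ahead to a possible restart: "A re-challenge may be considered in case of IMP discontinuation due to meeting one of the above stopping criteria", after a diagnostic evaluation and with the Medical Monitor's approval. It adds that "Additional visits to the site for un-scheduled laboratory samplings should be arranged in such a case", with laboratory tests by a local doctor as the alternative.

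Section 3.5 covers a subject who stops trial treatment for whatever reason after at least one dose. That subject is to be asked to attend the early termination visit and then to go on "participating in all trial assessments according to the protocol (with the exception of IMP administration) until the planned Week 52 visit". If that is not possible, the fallback is to ask permission to "continue collecting their weekly PS prescription and/or actual PS administration data once a month" by phone and to keep collecting adverse events. Section 4.9.2 adds: "All subjects will be asked to consent to be followed up even if they stop taking treatment early". SAP 4.1 likewise asks such subjects to stay in the trial after the EOT visit, without IMP.

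**The concern.** One event has two different prescribed consequences, and the sentence giving the harsher one cites the section giving the milder one. A subject who has left the trial cannot be re-challenged in it, so the two cannot both be followed.

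Three things are at stake if a site applies 2.2.2 literally:

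- The subject loses the re-challenge option in 6.6.2. With fewer doses, the subject may also fall below the 70% of planned doses that Section 2.2.5 ties to eligibility for the extension trial.
- Scheduled laboratory visits after EOT stop for a subject with a liver signal, in a trial with safety as its primary objective and 9 enrolled subjects (SAP Section 2). Missing values are not replaced (protocol 7.8).
- The Week 48 metabolic balance is not done, if it was still to come.

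The SAP assumes that subjects stay. SAP 9.4 tabulates subjects who continue visits after withdrawal and whether they complete extended follow-up. SAP 10 removes the 4-week follow-up limit from the definition of a treatment-emergent event, so adverse events found at continuation visits would count in the primary safety analysis.

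**Working it through.** There is no figure in the plan to reproduce. The check compares the rules, then bounds the data at risk.

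**Step 1: the rules side by side**

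| Source | What stops | What continues |
|---|---|---|
| Protocol 2.2.2 | Trial participation | Not stated; refers to 6.6.2 |
| Protocol 6.6.2 | IMP | Diagnostic evaluation, extra laboratory visits, possible re-challenge |
| Protocol 3.5 | IMP, any reason, after at least one dose | All assessments except IMP to planned Week 52, if the subject agrees |
| Protocol 4.9.2 | IMP | Follow-up, with consent |
| SAP 4.1 | IMP | Participation beyond EOT |

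Section 2.2.2 stands alone. Section 3.5 carves out no exception for subjects who meet a stopping rule. The withdrawal reasons in 3.5.1 do not name the 6.6.2 rules; the nearest are investigator judgements on safety and on medical considerations.

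**Step 2: scheduled visits lost under a literal reading**

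Let w be the week of last dose, taken on the 4-weekly visit grid. It is an assumption, because the documents give neither frequency nor timing of stopping-rule events.

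- EOT falls 4 weeks after the last dose (3.5.2, 5.2.8): week w + 4, with a window of ±1 week.
- Scheduled follow-up lost after EOT: 52 − (w + 4) = 48 − w weeks.
- Chemistry is taken at each 4-weekly visit (Table 1), so the visits lost number (48 − w)/4.

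| w | EOT week | Weeks lost (EOT window) | Chemistry visits lost |
|---|---|---|---|
| 4 | 8 | 44 (43 to 45) | 11 (Weeks 12 to 52) |
| 24 | 28 | 24 (23 to 25) | 6 (Weeks 32 to 52) |
| 36 | 40 | 12 (11 to 13) | 3 (Weeks 44, 48, 52) |
| 44 | 48 | 4 (3 to 5) | 1 (Week 52) |

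These are upper bounds, since 3.5 only asks subjects to stay and some would decline.

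**Step 3: the Week 48 balance**

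The EOT procedures in 5.2.8 include no metabolic balance. It is therefore lost for any last dose before the Week 48 balance, including w = 44 to 47, where EOT falls at Week 48 or later.

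**Step 4: what survives**

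- The EOT visit, with chemistry (5.2.8).
- Anti-drug antibody samples 4 and 8 weeks after EOT (5.1.11.1), at about w + 8 and w + 12.
- Early-termination colonoscopy or colonography after at least eight doses (5.2.8). With the first dose at Week 0 and none missed, doses given by week w number w + 1. At w = 4 that is 5, too few; at w = 7 it is 8, enough.
- Follow-up of a medical reason for withdrawal (3.5.1), of SAEs (6.4) and of deteriorating liver function (6.5).
- Possibly monthly parenteral support and adverse event data by phone (3.5).
- The triggering laboratory value, already counted in the worst-grade shift tables, which use scheduled and unscheduled values (SAP 9.8.3).

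**Step 5: who is covered**

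The text examined is protocol version 4, which applies to the 7 Belgian subjects: 7/9 = 78% of those enrolled. The 2 French subjects remain under version 3, whose text is not available here.

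**The case against.** The strongest reply is that the documents resolve the conflict themselves. The 2.2.2 sentence contains no criteria, so a site must open 6.6.2 to apply it and will find the correct instruction there. Section 4.6 also requires the individual stopping rules to be followed under 6.6.2. The protocol's change summary records a revision of 6.6.2 in version 3 that included restarting IMP, which suggests an outdated summary sentence beside deliberately revised operative text. This stands as a reason to expect little harm. It does not make the sentence correct.

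Second, the practical loss is small and its likelihood unknown. Harm needs a liver stopping event, a site that follows 2.2.2 over 6.6.2, and a subject who would otherwise have stayed. Among 9 subjects that may never happen. The shift tables cover only treatment and safety follow-up, so laboratory values after EOT would probably not enter them anyway. Both points stand. The laboratory loss falls on by-visit summaries and listings, and the week counts describe size given an event, not risk. Likewise, 78% is the share of subjects under version 4, not the share in danger.

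Third, 3.5.1 lets an investigator withdraw a subject for safety or medical reasons, and re-challenge is only discretionary. That is true, but those are case-by-case judgements. They do not support automatic removal of everyone who meets a rule.

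Finally, trial withdrawal and drug discontinuation are also mixed for malignancy: 3.5.1 lists it as a withdrawal reason, while 6.2.2 stops IMP and follows the subject. That is a separate question and does not weaken this correction.

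**Conclusion.** The concern holds. Section 2.2.2 misstates the section it cites and conflicts with protocol 3.5 and 4.9.2 and SAP 4.1. Neither redaction nor superseded text explains it. Confidence is high on the contradiction.

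The consequence is minor: late, off-drug, descriptive laboratory and balance data from any affected subject, plus the loss of a conditional re-challenge. The bounds in the working assume a last dose on the visit grid, EOT four weeks later, and a subject who would have agreed to stay. The finding is shown for version 4 only. It should be corrected because it is an operative instruction on handling subjects with a safety signal, and correcting it is cheap.

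**What to change.** Replace the sentence in 2.2.2 with wording such as: *A subject who meets an individual stopping rule stops IMP (Section 6.6.2, which also describes possible re-challenge) and is asked to continue trial assessments under Section 3.5.* This point requires no other section to change. The clinical stopping and re-challenge criteria stay with the sponsor.

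The cost is amendment handling under Section 9.6 for one sentence. No assessments are added, because 3.5 already plans them. An edit to version 4 would not reach the 2 French subjects under version 3.
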